3.1.2.1.3. Duration of Each Local Reaction

The duration of each local reaction will be calculated in days as the resolution date of reaction - start date of reaction + 1. Resolution of the event is the last day on which the event is recorded in the e-diary (or AE CRF) or the date the event ends if it is unresolved during the participant e-diary recording period (end date collected on the CRF) or AE stop date, whichever is longer, unless chronicity is established. If there is no known end date, the duration will be considered unknown and set to “missing.” Participants with no reported reaction have no duration.

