10.11.3. SoA – Substudy A (Phase 1/2)

Visit Identifier	A101	A102	A103	Notes
Visit Description	Vaccination	1-Month Follow-Up Visit	6-Month Telephone Contact	
Visit Window (Days)	Day 1	28 to 35 Days After Visit A101	175 to 189 Days After Visit A101	Day 1 = Day of Vaccination
Obtain informed consent	X			See Section 10.1.3 .
Assign participant number	X			See Section 6.3 .
Obtain demography and medical history data* (including confirmed COVID-19 diagnosis or asymptomatic positive SARS-CoV-2 test result [NAAT or antigen test])	X			* Include date of onset and resolution (if applicable).
Perform clinical assessment	X			Including, if indicated, a physical examination. Examinations and assessments must occur prior to vaccination. See Section 8.3.1 .
Measure height and weight	X			
Measure vital signs (including oral temperature)	X			Blood pressure and pulse rate; see Section 8.3.2 .
Confirm use of contraceptives (if appropriate)	X	X		See Section 10.4.3
Collect prior COVID-19 vaccine information	X			
Collect details of any influenza vaccine received in the prior 12 months	X			Include product name and date of administration.
Collect nonstudy vaccine information	X	X	X	See Section 10.11.8.7 .
Collect prohibited medication use		X	X	See Section 10.11.8.7.1 .
Confirm eligibility	X			See Section 10.11.7 . Ensure that the participant meets none of the temporary delay criteria as described in Section 5.5 .
Obtain randomization number and study intervention allocation	X			Do not randomize until eligibility is confirmed and the participant is present. See Section 6.3 .
Collect blood sample for immunogenicity assessment	~50 mL†	~50 mL		† Prior to vaccination.

PFIZER CONFIDENTIAL

CT02-GSOP Clinical Protocol Template Phase 1 2 3 4 (14 April 2023)

TMF Doc ID: 164.01

Page 91

Visit Identifier	A101	A102	A103	Notes
Visit Description	Vaccination	1-Month Follow-Up Visit	6-Month Telephone Contact	
Visit Window (Days)	Day 1	28 to 35 Days After Visit A101	175 to 189 Days After Visit A101	Day 1 = Day of Vaccination
Administer study intervention	X			See Section 10.11.8.1.1 .
Assess acute reactions for at least 30 minutes after study intervention administration	X			Must include time of onset.
Explain to the participant e-diary completion requirements and assist the participant with downloading the application or issue provisioned device if required	X			See Section 8.3.4 .
Provide thermometer and measuring device	X			

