Review reactogenicity e-diary data (daily review is optimal during the active diary period)	X			Days 1 through 7.
Review ongoing reactogenicity e-diary symptoms and obtain stop dates		X		See Section 8.3.4 .
Collect AEs and SAEs as appropriate	X	X	X	
Collect e-diary or assist the participant with deleting application		X		Ensure all e-diary data have been transferred prior to e-diary deactivation or removal of the app.

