- The investigator or appropriately qualified designee reviews the reactogenicity e-diary data online following vaccination to evaluate participant compliance and as part of the ongoing safety review. Daily review is optimal during the active diary period.

10.11.10.7.2. Visit A102 – 1-Month Follow-Up Visit (After Vaccination) – 28 to 35 Days After Visit A101

- Record AEs as described in [Section 8.4](#).
- Record nonstudy vaccinations as described in [Section 10.11.8.7](#).
- Record prohibited medication use as described in [Section 10.11.8.7.1](#).
- Verify understanding of and compliance with protocol requirements for contraception as described in [Section 5.3.1](#).
- Collect a blood sample of approximately 50 mL for immunogenicity testing.
- Review the participant's reactogenicity e-diary data. Collect stop dates of any reactogenicity e-diary events ongoing on the last day that the reactogenicity e-diary was completed and record stop dates in the CRF if required.
- If not already completed, collect the participant's e-diary or assist the participant with removing the study application from their own personal device.
 - Ensure all e-diary data have been transferred prior to e-diary deactivation or removal of the app.
- Record any AEs that occur within the 48 hours after the blood draw as described in [Section 8.4.1](#).

10.11.10.7.3. Visit A103 – 6-Month Telephone Contact – 175 to 189 Days After Visit A101

- Contact the participant by telephone.
- Record SAEs as described in [Section 8.4](#).
- Record nonstudy vaccinations as described in [Section 10.11.8.7](#).
- Record prohibited medication use as described in [Section 10.11.8.7.1](#).

- Complete the source documents.
- The investigator or an authorized designee completes the CRFs.

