3.1.2.2. Systemic Events Within 7 Days After Vaccination

Systemic events, including fever, fatigue/tiredness, headache, chills, vomiting, diarrhea, new or worsened muscle pain, and new or worsened joint pain, are reported from Day 1 through Day 7 after vaccination, where Day 1 is the day of vaccination with any study intervention. The derivations for the systemic events as described below will be handled similarly to the way that local reactions are handled for the presence for each participant, severity level, duration, onset day, and presence of severe systemic event on each and any day.

1. Presence (yes or no) of each systemic event on any day (Day 1 through Day 7) after vaccination.
2. Presence (yes or no) of any systemic event on any day (Day 1 through Day 7) after vaccination.
3. Maximum severity of each systemic event on any day (Day 1 through Day 7) after vaccination.
4. Maximum severity of any systemic event on any day (Day 1 through Day 7) after vaccination.
5. Duration of each systemic event after vaccination.
6. Onset day of each systemic event after vaccination.

The grading scale for systemic events is provided in the protocol. However, the derivation of severity of each systemic event on each day should be based on the maximum severity reported from the e-diary or AE CRF, if data are reported from both sources; or the e-diary alone if not reported from the AE CRF.

Fever is defined as a temperature of $\geq 100.4^{\circ}\text{F}$ ($\geq 38.0^{\circ}\text{C}$). The highest temperature for each day will be recorded in the e-diary. Any measure with degrees Fahrenheit will be converted to degrees Celsius for analysis. For reporting purposes, fever will be analyzed using the following temperature ranges:

- Mild (≥ 38.0 to 38.4°C from the e-diary or mild grade from the AE CRF);
- Moderate (>38.4 to 38.9°C from the e-diary or moderate grade from the AE CRF);
- Severe (>38.9 to 40.0°C from the e-diary or severe grade from the AE CRF);
- Grade 4 ($>40.0^{\circ}\text{C}$ from the e-diary or severe grade from the AE CRF, and documented $>40.0^{\circ}\text{C}$ via CRF query or other sources).

Any temperature that is confirmed as incorrect will use the correct temperature for analysis and those for which the correct temperature is unknown will not be included in the analysis.

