6.1.3.2. Supplementary Analysis

To support the assessment of reactogenicity, the endpoints below, as specified in [Section 3.1.2.1](#) and [Section 3.1.2.2](#), will be summarized per the supplementary analysis with the same analysis population:

- Duration (days) of each local reaction and each systemic event after vaccination.
- Onset day of each local reaction and each systemic event after vaccination.

The presentation of the results will include a basic descriptive summary without the 95% CIs for each vaccine group.

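### Reactions with no known end date are dropped from the duration summary, so any that are still unresolved bias the reported mean and maximum duration low

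*SAP*

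**What the plan says.** - **Duration rule.** SAP 3.1.2.1.3 takes resolution date minus start date plus 1. Resolution is the last day the event is recorded, the end date on the CRF if the event outlasts the diary, "or AE stop date, whichever is longer, unless chronicity is established". The SAP does not say what counts as chronicity or what duration is then used. For an event without an end date: "If there is no known end date, the duration will be considered unknown and set to" missing.
- **Systemic events.** SAP 3.1.2.2 treats these like local reactions and lists "Duration of each systemic event after vaccination" among the derived variables.
- **Output.** SAP 6.1.3.2 lists "Duration (days) of each local reaction and each systemic event after vaccination" as a supplementary analysis, summarized descriptively by group without confidence intervals. Both sensitivity analyses in SAP 6.1.3.3 concern maximum severity.
- **Scheduled collection.** The schedule of activities (Protocol 10.11.3) has the row "Review ongoing reactogenicity e-diary symptoms and obtain stop dates" with a single mark. The table is broken in the text, but the mark reads as A102, whose window is "28 to 35 Days After Visit A101". The A102 procedures (Protocol 10.11.10.7.2) agree: "Collect stop dates of any reactogenicity e-diary events ongoing on the last day that the reactogenicity e-diary was completed". The A103 telephone contact (Protocol 10.11.10.7.3) covers SAEs, nonstudy vaccines and prohibited medication, not reactogenicity stop dates.
- **Other routes.** Protocol 8.3.4 obliges the investigator to obtain stop dates and names no last visit. It also says diary data need not be entered as AEs. Protocol 8.1.1 adds telehealth collection, and 8.4.1 continues AE follow-up until the event resolves or stabilizes.

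**The concern.** Whether a duration is missing depends partly on the duration itself. The longer a reaction lasts, the less likely it is to have an end date when the data are analysed. Setting it to missing removes it from the mean, the SD and the maximum, and no rule puts it back, whether by censoring, by a minimum duration or by a count of unresolved events.

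Duration supports the primary safety objective, in people aged 65 and over. The events include fatigue and new or worsened muscle and joint pain, for which persistence is a reasonable possibility. A reader would want to see a reaction that lasted a month or more, and under this rule it could be absent from the duration table. If the unresolved share differs between groups, so does the bias.

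**Working it through.** The documents state no figure for reaction duration or for the share unresolved, so there is nothing to reproduce. What can be checked is the direction of the bias and its size as a function of that share.

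**Shortest possible duration of a reaction still present at A102.** The inputs are onset on Day 1 to Day 7 (the diary period) and A102 held 28 to 35 days after Day 1, that is on Day 29 to Day 36. By the SAP formula, minimum duration = visit day − onset day + 1.

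| Onset | A102 on Day 29 | A102 on Day 36 |
|---|---|---|
| Day 1 | 29 − 1 + 1 = 29 | 36 − 1 + 1 = 36 |
| Day 7 | 29 − 7 + 1 = 23 | 36 − 7 + 1 = 30 |

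The minimum is therefore 23 to 36 days for a visit held within the protocol window.

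**Shortfall in the mean.** Let p be the share of reactions unresolved at A102 with no end date, m_r the mean of the resolved reactions, and m_u the minimum duration of the unresolved ones. The plan reports m_r. The mean of all reactions is at least (1 − p)·m_r + p·m_u. The shortfall is therefore at least p·(m_u − m_r).

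With m_r = 3 days (assumption), m_u − m_r runs from 23 − 3 = 20 to 36 − 3 = 33 days:

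| p (assumption) | Shortfall of at least (days) |
|---|---|
| 0% | 0 |
| 0.5% | 0.10 to 0.17 |
| 1% | 0.20 to 0.33 |
| 2% | 0.40 to 0.66 |
| 5% | 1.00 to 1.65 |

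At p = 1%, taking m_r as 2 days gives 0.21 to 0.34, and as 5 days 0.18 to 0.31, so the result depends little on m_r. As a guide to scale, if all 150 participants in a group reported a given reaction and one were unresolved, p would be 1/150 = 0.67% and the shortfall at least 20/150 = 0.13 to 33/150 = 0.22 days.

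**Median.** With resolved durations drawn from an assumed geometric distribution with mean 3 days, and unresolved reactions added at 30 days, the median stayed at 2 days for p up to 10%.

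**Maximum.** One unresolved reaction is enough to make the reported maximum too low, if it has lasted longer than every reaction with an end date.

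**The case against.** The strongest reply is that A102 is only the last scheduled collection point. The duty in Protocol 8.3.4 has no cut-off visit. Protocol 8.3.4.2 and 8.3.4.3 have persisting reactions reported and entered in the CRF. A reaction recorded as an AE is followed to resolution or stabilization, and SAP 3.1.2.1.3 accepts the AE stop date. This stands. A reader might infer that every reaction present at A102 loses its duration, or that no reported duration can exceed the A102 window; the documents do not support either. What remains is narrower. The AE route need not cover every diary reaction. SAP 6.1.3.1 times the reactogenicity analysis only at the final immunogenicity analysis, on data through A102 (SAP 7.1.1), whereas SAP 6.1.4.1 adds the final database release for AEs. No update of durations with later dates is stated.

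Two more inferences go too far. One is that all long reactions are dropped: a reaction ending between Day 8 and A102 keeps its full duration, so one lasting 20 days counts as 20. The other is that chronic events are excluded: the text leaves their duration undefined, which is an ambiguity and not an exclusion.

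A missing end date may also come from an incomplete diary or loss to follow-up, and such a reaction need not be long. That is correct, and it is a reason to separate the causes. The number n in the duration table (SAP 5.2.2), set against the number reporting the reaction, would reveal missing durations but not their cause.

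Finally, the analysis is supplementary and descriptive, and no success criterion uses it. That stands and limits the weight of the point.

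**Conclusion.** The point holds in a conditional form. If any reaction is unresolved and no end date is obtained by any route, the plan drops it, and the reported mean and maximum are biased low, given that resolved reactions are shorter on average than the 23 to 36 days that a reaction ongoing at A102 has already lasted. If there are none, there is no bias.

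The size cannot be derived from the documents. The shortfalls above rest on assumed values for the unresolved share and for the mean of resolved reactions. Within them the effect runs from a fraction of a day to between one and two days in the mean, with little or no effect on the median. It would be too strong to infer that a group with persistent reactions must look as good as one without: presence and maximum severity, the main reactogenicity results, do not depend on the end date. This is a low-impact point with a cheap remedy.

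**What to change.** In SAP 3.1.2.1.3, and through it 3.1.2.2:

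- Replace the set-to-missing rule with a minimum duration, right-censored at the last date the reaction was known to be present.
- Show, for each event and group, the number ongoing at last contact, separately from the number whose end date is unknown for other reasons.
- When the longest duration is censored, report the maximum as ≥ x days. Label any mean that includes minimum durations as a lower bound.
- State what counts as established chronicity and what duration is then used.

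Kaplan-Meier medians and upper quantiles are an option, not a necessity, for a descriptive table.

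The cost is SAP wording and a small amount of programming on data already collected. No visit or procedure is added. Reported durations may become slightly longer.

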3.1.2.1.4. Onset Day of Each Local Reaction

The onset day of each local reaction will be derived. Onset day is defined as the first day of reporting any severity.

For the onset day of each local reaction, if the participant reports changes in severity of the local reaction, only the first day of reporting that specific local reaction will be counted.

3.1.2.2. Systemic Events Within 7 Days After Vaccination

Systemic events, including fever, fatigue/tiredness, headache, chills, vomiting, diarrhea, new or worsened muscle pain, and new or worsened joint pain, are reported from Day 1 through Day 7 after vaccination, where Day 1 is the day of vaccination with any study intervention. The derivations for the systemic events as described below will be handled similarly to the way that local reactions are handled for the presence for each participant, severity level, duration, onset day, and presence of severe systemic event on each and any day.

1. Presence (yes or no) of each systemic event on any day (Day 1 through Day 7) after vaccination.
2. Presence (yes or no) of any systemic event on any day (Day 1 through Day 7) after vaccination.
3. Maximum severity of each systemic event on any day (Day 1 through Day 7) after vaccination.
4. Maximum severity of any systemic event on any day (Day 1 through Day 7) after vaccination.
5. Duration of each systemic event after vaccination.
6. Onset day of each systemic event after vaccination.

The grading scale for systemic events is provided in the protocol. However, the derivation of severity of each systemic event on each day should be based on the maximum severity reported from the e-diary or AE CRF, if data are reported from both sources; or the e-diary alone if not reported from the AE CRF.

Fever is defined as a temperature of $\geq 100.4^{\circ}\text{F}$ ($\geq 38.0^{\circ}\text{C}$). The highest temperature for each day will be recorded in the e-diary. Any measure with degrees Fahrenheit will be converted to degrees Celsius for analysis. For reporting purposes, fever will be analyzed using the following temperature ranges:

- Mild (≥ 38.0 to 38.4°C from the e-diary or mild grade from the AE CRF);
- Moderate (>38.4 to 38.9°C from the e-diary or moderate grade from the AE CRF);
- Severe (>38.9 to 40.0°C from the e-diary or severe grade from the AE CRF);
- Grade 4 ($>40.0^{\circ}\text{C}$ from the e-diary or severe grade from the AE CRF, and documented $>40.0^{\circ}\text{C}$ via CRF query or other sources).

Any temperature that is confirmed as incorrect will use the correct temperature for analysis and those for which the correct temperature is unknown will not be included in the analysis.

3.1.2.3. Adverse Events and Serious Adverse Events

Standard algorithms for handling missing AE dates and missing AE severity levels will be applied as described in the Pfizer vaccine data standard rules. Completely missing AE start dates will not be imputed.

The following derivations (yes/no) will be included for each participant:

1. Any AE reported through 1 month after vaccination: If the AE started on the same day of vaccination, and the AE start time is before the vaccination time, then this AE will not be counted. Otherwise, if the AE start time is missing or after the vaccination time, the AE will be included.
2. Any related AE reported through 1 month after vaccination: This is similar to the above except only the related AE is included (excluding the related reactogenicity reported within 7 days after vaccination [[Section 3.1.2](#)]).
3. Any immediate AE (AE start time is within 30 minutes after vaccination) reported after vaccination: Only include AEs that started on the same day of vaccination and with a nonmissing AE start time that is within 30 minutes of vaccination. If the immediate AE is a related reactogenicity event, it would not be included as an immediate AE.
4. Any severe or life-threatening AE reported through 1 month after vaccination.
5. Any AE leading to study withdrawal after vaccination.
6. Any AE leading to death after vaccination.
7. Any SAE reported from vaccination throughout the substudy (including reactogenicity reported in the AE CRF during the e-diary collection period).
8. Any protocol-specified AESI reported from vaccination throughout the substudy. The following are protocol-specified AESIs based on AE PTs:
 - Confirmed diagnosis of influenza.
 - Confirmed diagnosis of RSV infection.
 - Confirmed diagnosis of myocarditis or pericarditis occurring within 4 weeks after vaccination. See PTs provided in [Section 3.5.3](#).
 - Confirmed COVID-19 diagnosis after Visit 1 through the end of the study (clinical signs/symptoms per [CDC¹](#) and positive SARS-CoV-2 NAAT or rapid antigen test result).

Variables 1 through 6 listed above will be derived with 2 approaches: excluding any reactogenicity (but not excluding reactogenicity SAEs) reported in the AE CRF during the e-diary collection period, and with no exclusion at all.

3.2. Secondary Endpoints

The secondary immunogenicity endpoints are similar to the primary immunogenicity endpoints except they are not applicable to Group 1 or Group 2.

3.3. Other Endpoints

3.3.1. Immunogenicity Results Fold Rise

As immunogenicity is measured both before vaccination and 1 month after vaccination, the fold rise of each assay result will be derived as the ratio of postvaccination results to prevaccination results for each participant. When calculating a fold rise, if assay results are $< \text{LLOQ}$, the assay results will be converted to $0.5 \times \text{LLOQ}$, except when the prevaccination assay result is $< \text{LLOQ}$ while the postvaccination result is $\geq \text{LLOQ}$, in which case the prevaccination value will be set to the LLOQ.

3.3.2. RSV A/B

RSV A/B NT will be derived for the geometric mean of RSV A and RSV B NTs measured at each blood sampling time point for each participant.

RSV A/B NT fold rise will be derived for the geometric mean of RSV A and RSV B NT fold rises from before vaccination to after vaccination for each participant.

3.3.3. HAI Seroprotection

HAI seroprotection is defined as an HAI titer $\geq 1:40$. This will be derived for each participant at Visit A101 and Visit A102 for each strain.

3.3.4. HAI Seroconversion

HAI seroconversion from before vaccination to after vaccination (Visit A102) will be defined for each participant for each strain as follows:

- If the HAI titer is $< 1:10$ before qIRV administration, seroconversion is achieved if the postvaccination titer is $\geq 1:40$.
- If the HAI titer is $\geq 1:10$ before qIRV administration, seroconversion is achieved if the fold rise in titer from before qIRV administration to after vaccination is ≥ 4 .

3.3.5. SARS-CoV-2 Seroresponse

SARS-CoV-2 seroresponse after vaccination will be defined for each participant for each strain as follows:

- If prevaccination results are $\geq \text{LLOQ}$, seroresponse is achieved if there is a ≥ 4 -fold rise from prevaccination results.
- If prevaccination results are below LLOQ, seroresponse is achieved if the postvaccination titer is $\geq 4 \times \text{LLOQ}$.

3.3.6. RSV Seroresponse

RSV seroresponse after vaccination will be defined for each participant for subgroup A and subgroup B respectively:

- If prevaccination results are \geq LLOQ, seroresponse is achieved if there is a ≥ 4 -fold rise from prevaccination results.
- If prevaccination results are below LLOQ, seroresponse is achieved if the postvaccination titer is $\geq 4 \times$ LLOQ.

3.4. Baseline Variables

3.4.1. Baseline Definition

Day 1 is defined as the day of Vaccination 1. Measurements or samples collected prior to Vaccination 1 on Day 1 are considered the baseline data for the assessments.

